5.2 Definition of Dose-Limiting Toxicity

DLT for dose-escalation purposes will be determined during the first 8 weeks of combination therapy (56 days from start of combination, starting cycle 1 day 1 of ipilimumab and decitabine) during the induction phase only. A DLT will be defined as any of the following toxicities that are determined to be *at least possibly* related to treatment with combination ipilimumab and decitabine and not related to underlying disease or intercurrent illness or to decitabine alone. Adverse events that occur after the first 8 weeks will also be evaluated by the investigator and may be considered dose limiting depending on the clinical scenario. Events will be graded by CTCAE v5.0 criteria.

DLTs include:

- Any study treatment related death (not due to disease or intercurrent illness).
- Acute GVHD that is an overall grade III or higher (see [Appendix B](#))
 - Exception: For skin GVHD alone, must be an overall grade II with at least stage 3 involvement or higher to be considered a DLT (skin GVHD that is stage 1-2 will not be considered a DLT).
- Grade 3 or higher non-hematologic toxicity
 - Exceptions:
 - Fatigue, nausea, weight loss, electrolyte abnormalities managed by replacement or correction, endocrine abnormalities managed by replacement therapy, skin rash, and those attributable to GVHD (as above)
 - Infections will be considered a DLT if grade 4 or higher or grade 3 that does not recover to grade 1 within 4 weeks
- Admission and IV antibiotics for neutropenic fever without sepsis or severe complication will not be considered a DLT (this is a frequent complication of underlying disease and of decitabine therapy)
- Grade 3 immune-related adverse events (e.g. diarrhea, pruritus, rash, endocrinopathies) that respond to corticosteroids and improve to grade 1 or less within 4 weeks will NOT count as DLTs. Optional biopsy of affected organs will be encouraged to help determine whether the immune-related condition is due to direct effects of ipilimumab versus GVHD.
- Grade 3 ipilimumab infusion reactions; a second consecutive occurrence or grade 4 or high infusion reaction will be considered a DLT.
- Grade 4 or higher hematologic toxicity will be considered a DLT if patients do not recover their absolute neutrophil count to $\geq 500 \times 10^9/L$ or platelet count to $\geq 25,000 \times 10^9/L$, at the end of the DLT window, with a hypocellular marrow and absence of

underlying disease.

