6.4.6 Other Immune-mediated Adverse Reactions, Including Ocular Manifestations

Ocular inflammation, manifested as grade 2 or grade 3 episcleritis or uveitis, was associated with concomitant diarrhea in a few subjects (<1%) and occasionally occurred in the absence of clinically apparent GI symptoms. Other presumed immune-related AEs reported include, but were not limited to, arthritis/arthralgias, pneumonitis, pancreatitis, autoimmune (aseptic) meningitis, autoimmune nephritis, pure red cell aplasia, noninfective myocarditis, polymyositis, and myasthenia gravis, of which were individually reported for <1% of subjects.

The following clinically significant immune-mediated adverse reactions were seen in less than 1% of ipilimumab-treated patients in Study 1: nephritis, pneumonitis, pulmonary granuloma resembling sarcoidosis, meningitis, pericarditis, uveitis, iritis, ITP, neutropenia and hemolytic anemia.

Across the clinical development program for ipilimumab, the following likely immune-mediated adverse reactions were also reported with less than 1% incidence: myocarditis, angiopathy, temporal arteritis, vasculitis, polymyalgia rheumatica, conjunctivitis, blepharitis, episcleritis, scleritis, leukocytoclastic vasculitis, erythema multiforme, psoriasis, pancreatitis, arthritis, and autoimmune thyroiditis.

Permanently discontinue ipilimumab for clinically significant or severe immune-mediated adverse reactions. Initiate systemic corticosteroids at a dose of 1 to 2 mg/kg/day prednisone or equivalent for severe immune-mediated adverse reactions.

Administer corticosteroid eye drops to patients who develop uveitis, iritis, or episcleritis. Permanently discontinue ipilimumab for immune-mediated ocular disease that is unresponsive to local immunosuppressive therapy.

Overall, immune-related AEs commonly started within 3 to 10 weeks from first dose, were successfully managed in most instances by omitting doses, discontinuing dosing, and/or through administering symptomatic or immunosuppressive therapy, including corticosteroids, as mentioned above and detailed in Section 7. Immune-related AEs generally resolved within days to weeks in the majority of subjects.

There have also been reports of encephalitis.

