13. STATISTICAL CONSIDERATIONS

13.1 Study Design/Endpoints

This is an open-label phase 1 study using a standard 3+3 dose-escalation design with planned dose escalation of ipilimumab in combination with decitabine, to define the safety profile and MTD (RP2D) in patients with R/R MDSAML with and without previous allogeneic HSCT. Two arms are planned. Arm A will include a cohort of patients who are post-transplant (patients who were transplanted by allogeneic HSCT at any time). Arm B will include a cohort of patients who are transplant naive (patients who never received allo-HSCT). Both cohorts will be tested at three different ipilimumab dose levels (dose level 0 (starting dose; first dose level): 3 mg/kg, dose level 1: 5 mg/kg, and dose level 2: 10 mg/kg). Three to six patients will be evaluated at each dose level per arm.

Please see section 5.1 for details on patient enrollment. We will demonstrate safety in the first dose level in patients on Arm B prior to enrolling patients onto Arm A. After safety is demonstrated at this first dose level, enrollment can then occur simultaneously without further delay or observation period. A dose de-escalation level (-1) will be allowed with ipilimumab at 1 mg/kg. Arm A does not need to complete dose escalation before Arm B if Arm B is able to move to dose-expansion; and vice versa. In the event that 0 of 3 patients in a dose level experience a DLT, the dose level may still be expanded to 6 evaluable patients based on observed toxicity at the current dose level at the discretion of the overall PI to capture patient safety prior to expanding.

Dose escalation will follow a standard 3+3 design exploring 3 dose levels of ipilimumab (starting at dose level 0, at 3 mg/kg) with decitabine (20 mg/m² daily x 5 consecutive doses). We will escalate to next dose cohort if 0/3 or 1/6 participants have a DLT during the first two cycles of combination therapy (cycles 1+2; first 8 weeks of combination therapy). If the rate of dose limiting toxicity (DLT) exceeds 30%, it is less likely that the dose of ipilimumab will be

dose-escalated. The table below provides the probability that the dose will be escalated, i.e., that 0 in 3 or 1 in 6 patients experience a DLT, given the true but unknown rate of DLT.

	True but unknown probability of DLT				
	0.10	0.20	0.30	0.40	0.50
P(escalate)	0.91	0.71	0.49	0.31	0.17

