The MTD will be the highest dose at which 1 or fewer of 6 patients experience a DLT. If no MTD has been established, then dose level 2 will be used in the dose expansion cohort as the recommended phase 2 dose (RP2D). Once an MTD (or RP2D) has been established an expansion cohort will be enrolled for each arm. For a given arm, if all 3 dose cohorts are filled to 6 patients, then a 6 patient expansion will be added. If 2 or fewer dose cohorts are filled to 6 patients, then a 12 patient expansion will be added so that no more than 24 patients (dose escalation + expansion) will be treated on a given arm. Patients will be monitored for DLTs during the first 8 weeks of combination therapy (56 days from start of combination) during the induction phase only. If a patient experiences disease progression in cycle 1, the patient will be evaluable for DLT if the patient completes a minimum of 28 days. Any patient who does not complete cycle 1 for any reason other than DLT will be considered non-evaluable for dose escalation decisions and will be replaced by an additional patient at that same dose level. Patients in cycle 2 will be assessed for DLT.

Safety and tolerability of decitabine plus ipilimumab will be evaluated by means of drug related DLT (defined as first 8 weeks of combination treatment with decitabine and ipilimumab), AE reports (following CTCAE V.5 criteria), physical examinations, and laboratory safety evaluations. These results will be tabulated overall and by dose level to examine their frequency, organ systems affected, severity, and relationship to study drugs.

The goal of the expansion cohort will be to further assess the tolerability of decitabine plus ipilimumab. Frequency of grade 3 or higher non-hematologic toxicities will be reported by arm and frequency of all grade immune-related adverse events will be reported by arm. Additionally, GVHD for the patients on the post-transplant arm will be estimated and reported with a 90% exact binomial confidence interval.

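### A patient can be counted as DLT-free after 28 days of a 56-day window, because nothing requires a day-56 status for those already off treatment

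*Combined protocol and SAP*

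**What the plan says.** Section 5.2 sets the period: "DLT for dose-escalation purposes will be determined during the first 8 weeks of combination therapy", counted as 56 days from cycle 1 day 1. Section 13.1 repeats the 56 days and ties escalation to them: "We will escalate to next dose cohort if 0/3 or 1/6 participants have a DLT during the first two cycles of combination therapy".

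Section 13.1 then defines who counts. For progression in cycle 1, "the patient will be evaluable for DLT if the patient completes a minimum of 28 days". The replacement rule is "Any patient who does not complete cycle 1 for any reason other than DLT will be considered non-evaluable", with replacement at the same dose level. One further sentence says that patients in cycle 2 are assessed for DLT. No rule is given for someone who completed cycle 1 and is no longer in cycle 2 treatment.

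Section 5.1 takes progressors off study at response assessments, the first being the marrow at days 24-28 of cycle 1, unless they tolerate treatment and benefit from it.

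For patients who have left:
- Section 5.6 provides a phone call every 3 months, and follow-up to resolution or stabilization for those removed for an unacceptable adverse event.
- The footnotes in section 10.1 describe the quarterly call as survival follow-up and place a clinical exam 3 months (plus or minus 1) after the last treatment.
- Sections 5.3, 7.3.3, 7.3.5 and 12.1 require sites to report DLTs, grade 3 or higher ipilimumab-related events, serious events, suspected immune-related events or GVHD, and grade 4-5 events.

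**The concern.** A cycle is 28 days, so a patient becomes evaluable halfway through the window on which escalation rests. That works only if someone establishes what happened in the second half. For a patient who stopped after cycle 1, or early in cycle 2, for a reason other than toxicity, the plan neither schedules that check nor makes it a condition of being counted.

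The MTD/RP2D is the primary objective, and each decision rests on 3 to 6 patients. One missed DLT can turn 1 of 3 into 0 of 3, or 2 of 6 into 1 of 6. Because the patient stays in the denominator, the error can run only toward escalation. The first Arm B cohort also controls the opening of Arm A, which section 5.1 delays because of possible toxicity after transplant.

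**Working it through.** **1. The plan's own table.** Under the 3+3 rule with every counted patient carrying the full 56-day DLT probability p,

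P(escalate) = (1-p)^3 + 3p(1-p)^2 x (1-p)^3.

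For p = 0.10, 0.20, 0.30, 0.40, 0.50 this gives 0.906, 0.709, 0.494, 0.309, 0.172. Section 13.1 prints 0.91, 0.71, 0.49, 0.31, 0.17. The table is correct, but it presumes a known 56-day status for everyone counted.

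**2. When early leavers are next seen.** Take a patient given only cycle 1 (ipilimumab day 1, last decitabine day 5), removed on day 28.
- Expedited reporting within 30 days of last administration ends at about day 31 to 35. After that, section 7.3.3 covers serious events at least possibly related.
- The exam at 2 to 4 months after day 5 falls at about days 66 to 127.
- The first quarterly call, 3 months after day 28, falls at about day 119.

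Both dated contacts come after day 56. A patient also dosed on cycle 2 day 1 (day 29) is better covered: expedited serious-event reporting runs to about day 59.

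**3. Counted DLT rate.** Three inputs are assumptions, since the documents give none of them: s, the share of 56-day DLT risk falling after day 28; f, the share of patients without a DLT who leave at day 28; and c, the share of post-exit DLTs that still reach the investigators. Leavers are given the same later risk as stayers. Then

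counted rate = p x [1 - s x f x (1-c)],

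which goes into the formula in step 1. Example: p = 0.40, s = 0.5, f = 0.3, c = 0.75 gives 0.40 x (1 - 0.0375) = 0.385 and P(escalate) = 0.334.

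Section 6.4.6 says "immune-related AEs commonly started within 3 to 10 weeks from first dose", that is, days 21 to 70. If onset were uniform over that span (an assumption), 7 of the 35 in-window days fall by day 28 and 28 fall after it, so s = 28/35 = 0.8. I use s = 0.5 and s = 0.8.

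| p | s | c | f = 10% | f = 20% | f = 30% |
|---|---|---|---|---|---|
| 0.30 | any | 1 | 0.494 | 0.494 | 0.494 |
| 0.30 | 0.5 | 0.75 | 0.502 | 0.510 | 0.517 |
| 0.30 | 0.5 | 0 | 0.525 | 0.557 | 0.589 |
| 0.40 | any | 1 | 0.309 | 0.309 | 0.309 |
| 0.40 | 0.5 | 0.75 | 0.317 | 0.326 | 0.334 |
| 0.40 | 0.5 | 0.5 | 0.326 | 0.343 | 0.360 |
| 0.40 | 0.5 | 0 | 0.343 | 0.378 | 0.415 |
| 0.40 | 0.8 | 0.75 | 0.322 | 0.336 | 0.350 |

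At 75% capture the tabulated increases run from 0.502 - 0.494 = 0.008 to 0.350 - 0.309 = 0.041, or about 0.01 to 0.04. The rows with c = 0 are bounds for their s and f, not expectations.

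**The case against.** The strongest reply is that the window is defined in calendar time, so every patient is meant to be monitored to day 56, and that known events do arrive. Non-fatal DLTs are mostly related grade 3 or higher events, and section 7.3.3 asks sites to email those that are ipilimumab-related, with no time limit. Section 5.3 has sites notify DLTs. Section 12.1 adds at least monthly calls and sign-off of each escalation. This stands in part: it confines the gap mainly to non-serious or not-yet-classified events in early leavers. But these routes act once a site knows of an event, and none prompts a site to ask before the escalation decision.

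Few patients may leave at day 28. Section 5.1 keeps progressors who benefit, and section 10.1 allows the next cycle without final marrow results in persistent disease. Leavers who miss a second ipilimumab dose may also carry less later risk than the model gives them. Both points stand and pull the size down.

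The RP2D does not hang on one step. Section 5.2 requires at least 6 patients at that dose, and section 5.3 keeps monitoring DLTs in expansion, with a discussion triggered at 2 or more of 6. This stands too.

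A reader might also infer that the recovery criteria in section 5.2 prove 28 days too short. Grade 3 immune-related events "that respond to corticosteroids and improve to grade 1 or less within 4 weeks will NOT count as DLTs", and "Infections will be considered a DLT if grade 4 or higher or grade 3 that does not recover to grade 1 within 4 weeks". That does not follow. An event starting on day 40 is settled only around day 68, for patients on treatment as well. It is a separate matter in the DLT definition and no evidence against the 28-day rule. It does mean that a day-56 contact alone would leave some events unclassified.

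**Conclusion.** The gap is real and worth closing, but its effect is modest. The plan allows an early leaver to be counted as DLT-free without a status at day 56, and any resulting error favors escalation. For one escalation step the increase is about 0.01 to 0.04 at 75% capture and zero at full capture. It depends on assumed values of leaver share (10 to 30%), timing (half to 80% of risk after day 28) and capture. Later checks lessen the effect on the final RP2D.

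Three stronger readings are not supported. The documents do not say that DLT monitoring stops at day 28 for progressors; the 56-day sentence is general. The P(escalate) table is not miscalculated. Nor can one conclude that the selected dose will be too high, since that would need the larger no-capture figures, which ignore the reporting routes above.

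**What to change.** Keep the rule that patients who do not complete cycle 1 for a non-DLT reason are replaced. Change the 28-day sentence in section 13.1 to:

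> A patient who completes cycle 1 and stops treatment before day 56 without a DLT is evaluable only if DLT status is ascertained through day 56, by a toxicity contact at day 56 and before the escalation decision. An event with onset by day 56 whose classification depends on the 4-week recovery criterion in section 5.2 is followed until it can be classified before that patient is counted DLT-free. Patients whose status cannot be determined are replaced.

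Report, per dose level, how many counted patients received only one ipilimumab dose in the window.

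The cost is one contact per early leaver, a possible short delay to an escalation decision, and occasional replacements. As an illustration, take p = 0.30 and s = 0.5, with 30% leaving at day 28 and one in five of those not assessable, so 0.30 x 0.20 = 0.06 of patients without an early DLT are replaced. The evaluable fraction is 0.15 + 0.85 x 0.94 = 0.949, or 1/0.949 = 1.05 patients per evaluable patient. The DLT rate among them is (0.15 + 0.15 x 0.94)/0.949 = 0.307, and P(escalate) = 0.481 against 0.494, which is slightly conservative.

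The cap needs a sentence. With all three levels filled, 3 x 6 + 6 = 24 already uses the whole allowance per arm. State whether replacements come out of the expansion cohort or do not count toward the cap.

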13.2 Sample Size/Accrual Rate

For each arm (Arm A and Arm B), assuming all dose cohorts are filled, the estimated sample will be at most 24. Hence the total estimated total sample size is at most 48 patients. The expansion cohort will be set at the MTD/RP2D. After the first dose level is assessed in Arm B (transplant naive), then we will then allow enrollment of patients onto Arm A. Further enrollment will occur in parallel with no observation period or delay between the start of therapy for each enrolled patient in either arm. We anticipate completing accrual within 24 months. 1-2 patients per month will be accrued.

Up to an additional 12 months of follow-up will be required on the last participant to observe the participant's survival; for total study duration of 3 years.

PLANNED ENROLLMENT REPORT

Racial Categories	Ethnic Categories				Total
	Not Hispanic or Latino		Hispanic or Latino		
	Female	Male	Female	Male	
American Indian/ Alaska Native	0	0	0	0	0
Asian	2	2	0	0	4
Native Hawaiian or Other Pacific Islander	0	0	0	0	0
Black or African American	4	4	0	0	8
White	11	11	4	4	30
More Than One Race	2	2	1	1	6
Total	19	19	5	5	48

13.3 Stratification Factors

13.4 Analysis of Primary Endpoints

We will determine the MTD/RP2D of dose escalated ipilimumab in combination with decitabine in patients who are post allo-HCT and in patients who are transplant naive.

13.5 Analysis of Secondary Endpoints

Safety analyses will be based on the safety population, defined as all enrolled patients receiving at least 1 dose of ipilimumab. Categorical data will be presented as frequencies and percentages. All tests of treatment effects will be conducted at a 2-sided alpha level of 0.05, unless otherwise stated. All tests of interactions will be conducted at a 2-sided alpha level of 0.1, and all CIs will be given at a 2-sided 95% level, unless otherwise stated. Patients who are registered to the study and have received at least one dose of ipilimumab on study will be evaluable for response.

Clinical response to treatment will be assessed following the 2003 IWG criteria for AML [6] and the 2006 IWG criteria for MDS [7]. Anti-leukemic activity will be described in terms of best overall response rate (for AML, to include CR+CRi; for MDS, to include CR+marrow CR+PR+HI), PFS, OS, and remission duration. Time to event summaries will use the Kaplan-Meier method. We will separately evaluate the incidence of acute GVHD and chronic GVHD in patients in the post-allo-HCT cohort, and compare these events with response to treatment.

The focus of this trial is to establish the safety and RP2D of the combination; thus the biomarker studies should be considered exploratory. We will evaluate whether or not absolute lymphocyte count can predict for response for patients who receive combination treatment. ALC levels will be divided into: low (<1000 cells/ul) and normal/high (greater than or equal to 1000 cells/ul). We will compare the response and overall survival of patients with low ALC versus normal/high ALC using Kaplan-Meier estimates and differences will be assessed using log-rank test. We will further capture the absolute change in ALC level measured at baseline to end of cycle 2 (collected prior to dosing on cycle 3 day 1) for response and survival differences. For correlative laboratory tests, we will compare nonrandom measurements in an individual patient either across time (pre-treatment versus on-treatment) with a paired Student *t* test. OS will be censored at the date of last contacts.

REFERENCES

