- **Priming Phase** (Lead- In): The priming phase includes decitabine alone at 20 mg/m² given daily for 5 consecutive doses starting on days 1-5 on a 28 day cycle to provide priming and disease control. Hypomethylating agents, such as decitabine have been tested in the post allo-HCT setting with evidence of safety and tolerability [57-59] including at the same dose proposed in this study.
- **Induction Phase** (cycles 1-4): Cycles 1 through 4 will include treatment with decitabine 20 mg/m² daily for five consecutive doses on days 1-5 plus ipilimumab (given per dose level) on day 1 on a 28 day cycle. There will be three dose escalation levels tested: 3.0 mg/kg (starting dose), 5.0 mg/kg, and 10.0 mg/kg. There will be a dose de-escalation level provided (1.0 mg/kg). Pharmacokinetic data generated from the initial pilot study demonstrated that higher doses of ipilimumab correlated with increased ipilimumab exposure and that those doses may be sufficient to saturate CTLA-4 binding sites [5]. The starting dose level of 3.0 mg/kg was tested in the phase 1b study for relapsed hematologic malignancies after allo-HCT with demonstration of safety and tolerability [4]. There was evidence of preliminary clinical activity (discussed in Section 2.4 in detail) in this study at 10 mg/kg but with evidence of immune related adverse events and GVHD in some cases. Thus we will also test the dose of 5.0 mg/kg.
- **Maintenance Phase** (cycles 5-12): Cycles 5 through 12 will include treatment with decitabine 20 mg/m² daily for five consecutive doses on days 1-5 on a 28 day cycle. Ipilimumab will continue on day 1 every 8 weeks for a total of 4 doses.

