- There will be three phases: priming, induction and maintenance
- Hydroxyurea may be used to control leukocytosis
- **Lead In: Priming phase with decitabine alone**
 - **Treatment:** Decitabine 20 mg/m² IV daily over 60 minutes (+/- 15 minutes) x 5 consecutive doses on **days 1-5** given per institutional guidelines
 - **Pre-medication prior to chemotherapy:** per institutional standards
 - Supportive medication such as allopurinol or equivalent should be considered in patients with white blood cell counts $> 10 \times 10^9 / L$ to reduce risk of tumor lysis syndrome.
 - Clinic visits on day 1 and day 15 (+/- 3 days)
 - Labs on day 1 and day 15 (+/- 3 days)
 - Research blood and aspirate collection at the end of the lead in period on a day between days 24-28 (see correlative calendar in [section 10.2](#)).
 - Adverse event evaluation:
 - **Intolerability during priming phase:** If a patient experiences unexpected intolerance to decitabine during the lead in that cannot be ameliorated by supportive care measures, then that patient will not continue on trial and will be replaced.
 - **Graft versus host disease (GVHD):** If there is evidence of acute GVHD that requires the use of systemic corticosteroids agents during the lead in, then the patient will be taken off study due to concern for safety with checkpoint blockade and replaced.
- **Cycles 1-4: Induction phase with combination decitabine and ipilimumab**
 - **Pre-Treatment Requirements**
 - Hematologic criteria to start cycle 1: None required
 - Hematologic criteria to start cycle 2:
 - If there is persistent disease (e.g. peripheral blasts, any marrow disease, persistent leukemia cutis or other form of extramedullary disease) at the time of disease response evaluation at the end of cycle 1, then there are no hematologic requirements to start cycle.
 - In the absence of disease, patients must have an absolute neutrophil count $\geq 500 \times 10^9 / L$ or platelet count to $\geq 25,000 \times 10^9 / L$ to proceed; otherwise administration of treatment will be delayed.
 - Hematologic criteria to start cycle 3:
 - If there is persistent disease (e.g. peripheral blasts, any marrow disease, persistent leukemia cutis or other form of extramedullary disease) at the time of disease response evaluation at the end of cycle 2, then there are no hematologic requirements to start cycle.

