 - At the time of response assessments, patients with evidence of disease progression will come off study unless they have evidence of clinical benefit (i.e. improvement in transfusion frequency or peripheral blast reduction). Patients with evidence of disease progression may be allowed to stay on study if deriving clinical benefit with approval from the overall PI as there may be a delayed response with immunotherapy.
 - Additional maintenance dosing (following the same schedule of ipilimumab dosed on day 1 every other cycle with monthly decitabine) for patients with clinical benefit at completion of maintenance therapy will be considered with Overall PI until progression or unacceptable toxicity.

Regimen Description					
Agent	Premedications; Precautions	Dose	Route	Schedule	Cycle Length
Decitabine	Anti-emetic agent per institutional guidelines (i.e. compazine 10 mg injection or equivalent as slow push at a rate not to exceed 5 mg/min per institutional standards given 30 minutes [+/- 15 minutes] prior to chemotherapy)	20 mg/m ² (reconstituted and mixed per institutional guidelines)	Recommend giving decitabine first prior to ipilimumab. IV over 60 minutes [+/- 15 minutes].	Days 1-5 every 4 weeks	
Ipilimumab	None unless history of prior reaction Please see section 6.3 for recommendations for hypersensitivity precautions	1, 3 (starting dose level), 5, or 10 mg/kg	IV over 90 minutes (not bolus or IV push) [+/- 15 minutes]. Administer after decitabine infusion is completed (any time within four hours after infusion completion).	Day 1* every 4 weeks during induction and every 8 weeks during maintenance	28 days (4 weeks)

*Ipilimumab does not start until cycle 1

Please also refer to [section 6](#) for dose delay guidelines.

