5.5 Duration of Therapy

Duration of therapy will depend on individual response, evidence of progression, and tolerance. In the absence of treatment delays due to adverse events, treatment (including priming, induction and maintenance) may continue for up to 12 cycles of combination therapy or until one of the following criteria applies:

- Disease progression (as defined by ELN 2017 criteria for AML and by IWG criteria for MDS). As T-cell infiltration of the tumor can look like progressive disease, please

discuss the results of radiographic assessments (for extramedullary disease) showing progressive disease with the overall PI before removing a patient from the study for disease progression.

- Intercurrent illness that prevents further administration of treatment,
- Unacceptable adverse event(s) requiring permanent stopping of both ipilimumab and decitabine
- Patient decides to withdraw from the study
- Pregnancy
 - All women of child bearing potential should be instructed to contact the investigator immediately if they suspect they might be pregnant (e.g., missed or late menstrual period) at any time during study participation.
 - The investigator must immediately notify CTEP in the event of a confirmed pregnancy in a patient participating in the study.
- General or specific changes in the patient's condition render the patient unacceptable for further treatment in the judgment of the investigator.
- Termination of the study by sponsor.

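### The safety population requires an ipilimumab dose, so patients given protocol decitabine who leave during the lead-in are missing from the planned adverse event tables

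*Combined protocol and SAP*

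**What the plan says.** Section 13.5 sets two populations by the same condition. For safety: "Safety analyses will be based on the safety population, defined as all enrolled patients receiving at least 1 dose of ipilimumab". For response: "Patients who are registered to the study and have received at least one dose of ipilimumab on study will be evaluable for response". Section 13 defines no set of all treated patients and no separate summary of the lead-in.

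Treatment begins before that condition can be met. Section 2.3 describes priming decitabine as "given daily for 5 consecutive doses starting on days 1-5 on a 28 day cycle to provide priming and disease control", and the footnote to the regimen table in section 5.1 says "Ipilimumab does not start until cycle 1". Section 5.5 counts the lead-in as treatment: "treatment (including priming, induction and maintenance) may continue for up to 12 cycles of combination therapy".

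Section 5.1 names two ways out of the lead-in. For intolerance of decitabine that supportive care cannot relieve, "then that patient will not continue on trial and will be replaced". For acute GVHD needing systemic corticosteroids, "then the patient will be taken off study due to concern for safety with checkpoint blockade and replaced".

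On the safety tables, section 13.1 says: "These results will be tabulated overall and by dose level to examine their frequency, organ systems affected, severity, and relationship to study drugs".

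**The concern.** Both study drugs are given under protocol, and the safety tables are meant to show the relationship of events to both. Yet the patients who could not tolerate the first drug never meet the entry condition for those tables. The exclusion is not neutral: two of the exits are defined by toxicity or GVHD, and the patients concerned are replaced by others who may go on to ipilimumab.

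At stake is the description of the regimen, not the dose decision. Priming is part of what a phase 2 trial would take forward. A reader of the planned tables could not tell how many patients started treatment and failed to reach the combination, or what adverse events those patients had.

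**Working it through.** **1. The plan's own figures.** Maximum sample size: 2 arms × (3 dose levels × 6 + 6 expansion) = 2 × 24 = 48, as section 13.2 states. The largest 90% exact half-widths for a proportion are 25.5 points at n = 12 and 20.9 points at n = 18, against the stated 25 and 21. No stated figure is in error on this point.

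**2. Who is counted where.** Sections 13.1 and 13.5 set beside the rest of the plan:

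| Patient or event | Planned AE tables | Elsewhere in the plan |
|---|---|---|
| Lead-in AE in a patient later given ipilimumab | In: the set is defined by patient, not by time window | AE evaluation at lead-in day 15 (10.1) |
| Exit for decitabine intolerance | Out | Reason on the CRF (5.5), routine AE reporting (7.4); no planned summary |
| Exit for steroid-requiring acute GVHD, Arm A | Out | Arm A GVHD estimate (13.1, 13.5), read as covering the whole arm |
| Death in the lead-in | Out | Event in OS and PFS from registration (11.1.2, 13.1); expedited report (7.3.3) |
| Other exit before cycle 1 | Out | Reason on the CRF (5.5) |

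What no planned summary shows is the intolerance exits and the non-GVHD adverse events of patients who never reach cycle 1.

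**3. How many patients.** The documents give no lead-in loss rate, so a = 3%, 7% and 15% per starter are assumed. Section 2.1 cites 7% 30-day mortality in untreated elderly AML on the same decitabine dose and schedule. That is another population and counts deaths only, so it is context and not an estimate.

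If losses are replaced until D = 48 patients have received ipilimumab:

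- Expected number left out = D × a/(1 − a)
- Chance of at least one = 1 − (1 − a)^D

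| a | Expected left out | Chance of at least one |
|---|---|---|
| 3% | 48 × 0.03/0.97 = 1.5 | 77% |
| 7% | 48 × 0.07/0.93 = 3.6 | 97% |
| 15% | 48 × 0.15/0.85 = 8.5 | >99% |

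If 48 is instead a cap on patients starting treatment, the expected number is 48a = 1.4, 3.4 or 7.2, with the same chances.

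**4. Illustration for safety (hypothetical count).** With 2 intolerance exits and 48 dosed patients, the section 13.5 set shows 0/48 such exits. An all-treated set shows 2/50 = 4.0% (exact 95% CI 0.5 to 13.7%).

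**5. Response.** With 18 dosed patients at the MTD/RP2D, expected losses are 18 × a/(1 − a) = 0.6, 1.4 and 3.2. Taking 4 responders as an example, 4/18 = 22.2% becomes 4/19 = 21.1%, 4/20 = 20.0% or 4/21 = 19.0% with 1, 2 or 3 losses counted as non-responders. A shift of about 3 points at most is small beside the stated ±21 points.

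**The case against.** The strongest reply is that the restriction fits the purpose. The primary objectives (1.1) and section 13.1 concern the combination. Section 5.2 counts DLTs from the start of combination therapy and sets aside events due to decitabine alone. Decitabine is not escalated. An ipilimumab-dosed set is a proper set for combination safety. That stands, and is why it should be kept. It does not explain why it should be the only set when the tables are to show relationship to both drugs.

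Three stronger readings are tempting, and the documents do not support them:

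- *Lead-in deaths and GVHD disappear from the results.* OS and PFS run from registration within each arm, and GVHD is estimated for the post-transplant arm. Neither carries an ipilimumab condition. On their natural reading these events are counted, though not in the AE tables.
- *Priming toxicity is not captured.* Adverse events are recorded, deaths on study are reported regardless of cause, and lead-in events of patients who continue remain in the safety set.
- *The response rate is materially inflated.* The arithmetic shows a negligible effect. The lead-in has no response assessment, since its closing aspirate is for correlative work only. An all-starters response rate would also need a rule for exits other than death. The indeterminate class in Appendix D covers only AML deaths before the end-of-cycle-1 assessment.

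It is also fair to say that the size is hypothetical: the loss rates are assumed, and the chances above follow directly from them.

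**Conclusion.** The concern holds in a limited form. As written, section 13.5 leaves patients treated with protocol decitabine out of the planned adverse event tables, in part because of toxicity, and nothing else in section 13 restores them. At assumed loss rates of 3 to 15%, that is about 1.5 to 8.5 patients alongside 48 dosed.

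The conclusion rests on the literal wording of section 13.5 and on reading OS, PFS and the Arm A GVHD estimate as covering the whole arm. The true loss rate is unknown. The primary objective, the DLT and MTD rules and the sample size are untouched. This is a change that should be made to safety reporting; it does not threaten the trial's main conclusion.

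**What to change.** In section 13.5:

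- Define the safety population as all patients receiving any protocol drug, decitabine or ipilimumab.
- Tabulate adverse events by phase (lead-in, combination), and keep ipilimumab-dosed patients as the named subset for combination safety.
- Report, by arm, the number of patients who left during the lead-in and the reasons.
- Keep the ipilimumab-dosed set for response, and state beside it how many patients started therapy but never received ipilimumab.
- Align section 13.1, which assesses efficacy in patients enrolled at the MTD/RP2D, with the ipilimumab-dosed wording of section 13.5.

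The data needed are already collected: reasons for removal (5.5), deaths (7.3.3), adverse events (7.4) and the lead-in day 15 evaluation (10.1). The cost is analysis wording and one more table split. Treatment, DLT rules and sample size do not change. The downside is that some reported rates may look slightly worse.
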